### 8.3 AE Reporting Requirements

All AEs will be captured from the time of enrollment until subject participation has ended (i.e. completion of study or discontinuation). See section 8.3.1 for events that are not required to be reported to Edwards.

Pre-existing medical conditions or symptoms reported prior to subject enrollment will not be recorded as an AE. In the event there is a worsening in the pre-existing medical condition or symptoms due to the device or study-related procedure, then an AE must be recorded.

Death should not be recorded as an AE, but should be reflected as an outcome to another specific AE.

If known, the diagnosis for an AE should be recorded, rather than listing individual signs and symptoms.

All AEs will be reported in subject medical records, and the appropriate eCRF throughout the duration of the study, and will be followed until resolution, stabilization or study completion.

All SAEs and Device Deficiencies that might have led to a SAE should be reported to Edwards immediately, but not later than 3 calendar days after site study personnel's awareness of the event.

Other AEs must be reported to Edwards as soon as practical but no later than 10 working days of awareness.

Information must be entered into the electronic database or, when the electronic database is not available, reported directly to the Edwards Safety Officer. In the event that the EDC system is not in service, a paper copy of the AE CRF must be e-mailed to [contact] according to the timelines described above.

At the time of initial AE notification, the following minimal information must be provided:

- Subject ID
- AE term/diagnosis
- AE onset date

For selected events, the site might be requested to provide to Edwards (or designee) a copy of

anonymized supporting documentation (such as hospital record, laboratory results, autopsy results).

All AEs will be reviewed by the Edwards Safety Officer. Each AE will be assessed as to its relationship to the study device and/or implant procedure, whether it was anticipated or not anticipated, and whether it qualifies as an SAE and USADE.

Depending on the local requirements or following agreement between both parties, Edwards or the Principal Investigator will be responsible for performing safety reporting to the EC according to the relevant local regulatory requirements.

Edwards will be responsible for reporting to the National Competent Authority according to national requirements and in line with MEDDEV 2.7/3 (Serious Adverse Event Reporting) and/or MEDDEV 2.12-1 (Medical Device Vigilance System), as applicable.

### **8.3.1 Events that do not require reporting to Edwards**

For purposes of this study, the following events will not be required to be reported as AEs to Edwards, because they are normally expected to occur in conjunction with transcatheter valve implantation or are associated with customary, standard care of subjects undergoing THV implantation:

- Post-operative pain.
- Post-anesthesia emesis, nausea or headache (within 24 hours of procedure).
- Electrolyte imbalance without clinical sequelae following procedure, even if requiring correction.
- Low grade temperature increase ( $\leq 101^{\circ}\text{F}$  or  $38.5^{\circ}\text{C}$ ).
- Elevated white blood count, outside the standard laboratory normal value, without signs and symptoms of infection.
- Minor, localized tenderness, swelling, induration, oozing, etc. at incision / delivery system insertion site.
- Systolic or diastolic blood pressure changes that do not require treatment or intervention.
- Thrombocytopenia: does not become an AE until treatment is administered; Suspected heparin-induced thrombocytopenia should be reported.
- Hyperglycemia – The use of insulin in the post-operative period does not constitute hyperglycemia if during the index hospitalization. An elevated blood sugar of less than 250 mg/dL during the first 48 hours post-operative does not constitute hyperglycemia.
- Expected, non-clinically significant events such as non-significant lab variances.
- Dizziness: imprecise term commonly used to describe various symptoms such as faintness, giddiness, imbalance, lightheadedness, unsteadiness or vertigo without signs of TIA or stroke.

Additionally, pre-planned future surgical procedures not associated with the study procedure or device do not need to be reported.

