### 9.2 Potential Risks

The potential risks associated with this study can be grouped into two categories. First, there are the potential risks related to the overall procedure (standard cardiac catheterization, BAV and use of anesthesia). Second, there are the additional potential risks associated with the use of the SAPIEN 3 Ultra THV and SAPIEN 3 THV Systems.

Potential risks associated with the overall procedure including access, cardiac catheterization, local and/or general anesthesia:

- Allergic reaction to antithrombotic therapy or contrast medium or anesthesia
- Anemia
- Aneurysm
- Angina
- Arrhythmias including ventricular fibrillation (VF) and ventricular tachycardia (VT)
- Arteriovenous fistula or pseudoaneurysm
- Cardiogenic shock
- Compartment syndrome
- Death
- Dissection: aortic or other vessels
- Emboli, distal (air, tissue or thrombotic emboli)
- Hematoma
- Hypertension or hypotension
- Inflammation
- Myocardial ischemia or infarction
- Pain or changes at the access site
- Perforation or rupture of cardiac structures
- Perforation or rupture of vessels
- Pericardial effusion or cardiac tamponade
- Peripheral ischemia or nerve injury
- Pulmonary edema
- Renal insufficiency or renal failure
- Respiratory insufficiency or respiratory failure
- Syncope

- Vasovagal response
- Vessel spasm
- Vessel thrombosis/occlusion
- Vessel trauma requiring surgical repair or intervention

Additional potential risks associated with the TAVR procedure, the bioprosthesis, and the use of its associated devices and accessories include:

- Allergic/immunologic reaction to the implant
- Atrial fibrillation/Atrial flutter
- Bleeding requiring transfusion or intervention
- Cardiac arrest
- Cardiac failure or low cardiac output
- Cardiogenic shock
- Conduction system injury (defect) including atrioventricular block, which may require a permanent pacemaker
- Coronary occlusion
- Dissection, rupture, trauma of the aortic annulus and surrounding structures including ascending aorta, coronary ostia and ventricular septum
- Emergency cardiac surgery
- Hemolysis
- Infection, fever, septicemia, abscess, endocarditis
- Injury to mitral valve
- Mechanical failure of delivery system, and/or accessories, including balloon rupture and tip separation
- Silent cerebral ischemia, stroke, transient ischemic attack, cognitive impairment
- Structural valve deterioration (wear, fracture, calcification, stenosis)
- Valve deployment in unintended location
- Valve explants

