Bleeding	
Overt bleeding is defined as clinically obvious (visible bleeding and bleeding identified by imaging only). Examples of overt bleeding include:
 
 
• Pseudoaneurysm
 
• Retroperitoneal hematoma seen on CAT scan
 
• Visible access site hematoma
 
 
Actionable Bleeding is more bleeding than expected for clinical circumstance needing increased level of care like
 
 
• hospitalization
 
• medical/surgical intervention
 
• transfusions
 
 
Thresholds for reporting procedural bleeding for SAVR procedure is bloody chest tube output > 600 mL within any 24-hour period and for TF-TAVR >100 mL total EBL (Estimated Blood Loss) from access site. These are suggested as guidelines for Site reporting of Bleeding events and clinical judgement should be used in reporting bleeding events.
 
All post-procedural overt bleeding events must be reported including hematuria, melena, hematemesis, occult gastrointestinal bleeds or drop in Hgb with overt source of bleeding detected requiring transfusions etc.
 
If the reason for Hgb drop was other than due to the overt bleeding i.e. due to hemodilution, chronic iron deficiency anemia, this will not be considered as a bleeding event.
 
Note: Bleeding will be adjudicated per VARC-2 and BARC criteria.
	Sponsor
CABG	Coronary artery bypass graft surgery is a procedure performed to bypass partially or completely occluded coronary arteries with veins (commonly Great/Small Saphenous veins) and/or arteries (commonly Internal thoracic/Mammary artery) harvested from elsewhere in the body, thereby improving the blood supply to the coronary circulation supplying the myocardium (heart muscle).	Sponsor/ 2014 ACC/AHA Key Data Elements and Definitions for Cardiovascu lar Endpoint Events in Clinical Trials
Cardiac Arrest	Cardiopulmonary arrest or circulatory arrest is a sudden stop in effective blood circulation due to the failure of the heart to contract effectively or at all.	Sponsor / STS
Cardiac Tamponade	
Evidence of a new pericardial effusion associated with hemodynamic instability evident by:
 
 
1. Echo showing pericardial fluid and signs of tamponade such as right heart compromise, or
 
2. Systemic hypotension due to pericardial fluid compromising cardiac function
 
	VARC-2 / STS

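### Section 8.3.1 waives AE reporting on a peri-implant rationale, but 7 of its 11 items carry no time wording, none says that an SAE stays reportable, and the access-site item conflicts with the Appendix B bleeding rule

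*Combined protocol and SAP*

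**What the plan says.** Section 8.3 has AEs captured from enrollment until participation ends, and section 3 sets follow-up at five years. Section 8.3 then points to 8.3.1 for events that need not go to the sponsor. There, "the following events will not be required to be reported as AEs to Edwards", and the reason given is "because they are normally expected to occur in conjunction with transcatheter valve implantation", or that they belong to customary care of these patients. Eleven items follow. Some have their own limits; for example, "An elevated blood sugar of less than 250 mg/dL during the first 48 hours post-operative does not constitute hyperglycemia". The dizziness item has none. It describes dizziness as an "imprecise term commonly used to describe various symptoms such as faintness, giddiness, imbalance, lightheadedness, unsteadiness or vertigo without signs of TIA or stroke".

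Three other places bear on the list:

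- Section 8.3: "All SAEs and Device Deficiencies that might have led to a SAE should be reported to Edwards immediately", with an outer limit of 3 calendar days. The sentence does not mention 8.3.1.
- Section 9.2 names arrhythmia, hypotension, syncope and "Conduction system injury (defect) including atrioventricular block, which may require a permanent pacemaker" among the risks.
- Appendix B, under Bleeding, counts anything clinically visible as overt and gives a visible hematoma at the access site as an example. Of post-procedural overt bleeding it says that all such "events must be reported including hematuria, melena, hematemesis" and others. It makes no exception for minor bleeds.

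**The concern.** The reason for the waiver covers the days around the implant. The text that carries it out is, for most items, open-ended. A site that follows 8.3.1 literally could leave out a spell of faintness at year 3, or oozing from the access site the day after the procedure. A site that follows section 8.3 or Appendix B would report both. Neither would be breaking the protocol as it reads it.

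Three things are at stake. AE counts over follow-up may be incomplete. Minor-bleeding counts may differ between sites because of the rule they follow rather than what happened to patients, and a bleed that is not reported may not reach the VARC-2 and BARC adjudication promised in Appendix B. Sites may also be unsure whether the 3-day SAE duty applies to an event on the list. Section 9.1 says that long-term results with these valves are not known, so AE data from follow-up have some value here.

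**Working it through.** No sample size or error rate enters this point. The check is a classification of the 11 items, followed by a comparison of passages and one unit conversion.

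**1. Time and severity wording, item by item (section 8.3.1)**

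| Item | Time wording | Severity or consequence qualifier |
|---|---|---|
| Pain after the operation | tied to the operation, no duration | none |
| Emesis, nausea, headache after anesthesia | 24 hours | none |
| Electrolytes | tied to the procedure, no duration | no clinical sequelae |
| Temperature | none | upper limit |
| White count | none | no sign of infection |
| Access site | none | minor and localized |
| Blood pressure | none | not treated |
| Thrombocytopenia | none | until treated; suspected heparin-induced cases reportable |
| Glucose | 48 hours (insulin use: index stay) | below 250 mg/dL |
| Laboratory variances | none | not clinically significant |
| Dizziness | none | no TIA or stroke signs |

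Explicit window: 2. Tied to the procedure without a duration: 2. No time wording: 11 − 2 − 2 = 7. Items with a qualifier: 9 of 11. Items with an exception for SAEs: 0 of 11. With a year defined as 365 days (section 7.6), follow-up is 5 × 365 = 1,825 days.

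**2. Seriousness**

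Section 8.1 defines an SAE as an AE that meets a seriousness criterion, so SAEs are a subset of AEs. Section 8.3.1 waives reporting as AEs. Section 8.3 both refers to 8.3.1 and asks for all SAEs. Which rule wins is not stated. The overlap is not empty: pain after the operation has no qualifier and could prolong a hospital stay, and dizziness without TIA or stroke signs could lead to admission.

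**3. Dizziness**

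Section 8.3 asks for the diagnosis, where known, in place of the symptom. Arrhythmia, conduction defect and syncope have their own entries in Appendix B and are not on the list, so once diagnosed they are reportable. What remains is the undiagnosed symptom. Table 3 schedules a 12-lead ECG at screening and in the 48 hours after the procedure, and none later. The contacts at 6 months and at years 2 and 4 may be by telephone and include no physical assessment. Heart rate is taken at discharge, at 30 days and at years 1, 3 and 5. Between those visits, a complaint of faintness may be the only sign, and 8.3.1 does not ask for it. The line between waived faintness and syncope, which Appendix B defines to include a fainting spell, is also left to the site.

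**4. Access site**

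Visible oozing after the procedure is minor under 8.3.1 (not reported) and visible bleeding under Appendix B (reported). Swelling that proves to be a small visible hematoma falls under both in the same way. Appendix B's suggested threshold of more than 100 mL estimated blood loss applies to procedural bleeding, so it does not settle the post-procedural case.

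**5. Fever limit**

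(101 − 32) × 5/9 = 38.33°C. In the other direction, 38.5 × 9/5 + 32 = 101.3°F. A temperature above 38.33°C and up to 38.5°C is waived by the Celsius figure and not by the Fahrenheit figure, a band of 0.17°C.

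**The case against.** The best defence is that the list is narrower than it looks. Its opening sentence ties every item to the implant or to customary care, four items have a window or an anchor to the procedure, and nine have a severity or consequence qualifier. The SAE sentence in section 8.3 is unqualified. Monitors compare eCRFs with medical records (section 11.10), and section 8.1 allows the sponsor's safety and monitoring teams to find AEs in clinical records.

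Much of this stands, and it rules out several stronger readings that a reader might infer:

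- That a late conduction block or endocarditis is waived. It is not. The diagnosis is the AE, neither is on the list, and a raised white count is waived only without signs of infection.
- That access-site bleeding in general is waived. Only minor, localized signs are, and these arise mainly around the procedure.
- That the list waives SAEs. The text leaves the order of precedence open; it does not say this.
- That nobody but the sponsor's safety officer could see a listed event. The investigator, the monitors and record review remain, although a monitor who applies 8.3.1 as written has little reason to query a listed item.

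The defence does not answer three things. A rationale in an opening sentence is not a stop date, and the authors wrote explicit windows where they wanted them. The access-site item and Appendix B give opposite instructions for the same event. The two temperatures are not equal, though that point is editorial.

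**Conclusion.** The point holds as a drafting gap worth closing. Seven of 11 items have no time wording against five years of AE capture, none of the 11 has an SAE exception, one item contradicts Appendix B, and one limit has two values 0.17°C apart. Late faintness or lightheadedness without a diagnosis is the clearest case of an event that would go unreported.

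The consequence is limited to AE and minor-bleeding tabulations. The primary endpoint (death, conversion to surgery, moderate or severe paravalvular regurgitation at exit from the procedure room) and the secondary endpoints (major vascular complications, and valve migration or embolization, through discharge) are not on the list and are not directly affected.

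A reader might go further and say that reported rates are biased low by a material amount. The documents give no frequency for the waived events, so the size of any undercount cannot be estimated. The conclusion assumes only that some sites apply 8.3.1 as it is written.

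**What to change.** Amend the wording in four places:

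1. Open 8.3.1 with a sentence saying that the list applies only to events with onset during the index hospitalization that do not meet the SAE definition. Laboratory variances without clinical significance and untreated blood pressure changes may stay waived throughout, to keep the reporting load down.
2. In the dizziness item, extend the exception from TIA and stroke to signs of arrhythmia, conduction defect, hypotension or syncope. This covers the index stay, which the first change leaves within the waiver.
3. Reconcile the oozing and swelling item with the Appendix B rule on post-procedural overt bleeding, so that both give one instruction. Leave the guideline of more than 100 mL for procedural bleeding in place.
4. State one fever limit, with Celsius and Fahrenheit values that match.

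The cost is a protocol amendment and some extra non-serious AE entries, such as dizziness or low-grade temperature after discharge. No visit, test or endpoint changes.

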## 9 RISKS AND BENEFIT ANALYSIS

### 9.1 Potential Benefits

There are no guaranteed benefits from participation in this study. Information gained from this study may be of benefit to other people with the same medical condition in the future. The long-term results of using the SAPIEN 3 Ultra and SAPIEN 3 THVs are not known at the present time.

Implantation of the SAPIEN 3 Ultra and SAPIEN 3 THVs may result in improved valvular function, acute alleviation of symptoms related to AS, and improved quality of life in patients with intermediate operative risk of mortality.

### 9.2 Potential Risks

The potential risks associated with this study can be grouped into two categories. First, there are the potential risks related to the overall procedure (standard cardiac catheterization, BAV and use of anesthesia). Second, there are the additional potential risks associated with the use of the SAPIEN 3 Ultra THV and SAPIEN 3 THV Systems.

Potential risks associated with the overall procedure including access, cardiac catheterization, local and/or general anesthesia:

- Allergic reaction to antithrombotic therapy or contrast medium or anesthesia
- Anemia
- Aneurysm
- Angina
- Arrhythmias including ventricular fibrillation (VF) and ventricular tachycardia (VT)
- Arteriovenous fistula or pseudoaneurysm
- Cardiogenic shock
- Compartment syndrome
- Death
- Dissection: aortic or other vessels
- Emboli, distal (air, tissue or thrombotic emboli)
- Hematoma
- Hypertension or hypotension
- Inflammation
- Myocardial ischemia or infarction
- Pain or changes at the access site
- Perforation or rupture of cardiac structures
- Perforation or rupture of vessels
- Pericardial effusion or cardiac tamponade
- Peripheral ischemia or nerve injury
- Pulmonary edema
- Renal insufficiency or renal failure
- Respiratory insufficiency or respiratory failure
- Syncope

- Vasovagal response
- Vessel spasm
- Vessel thrombosis/occlusion
- Vessel trauma requiring surgical repair or intervention

Additional potential risks associated with the TAVR procedure, the bioprosthesis, and the use of its associated devices and accessories include:

- Allergic/immunologic reaction to the implant
- Atrial fibrillation/Atrial flutter
- Bleeding requiring transfusion or intervention
- Cardiac arrest
- Cardiac failure or low cardiac output
- Cardiogenic shock
- Conduction system injury (defect) including atrioventricular block, which may require a permanent pacemaker
- Coronary occlusion
- Dissection, rupture, trauma of the aortic annulus and surrounding structures including ascending aorta, coronary ostia and ventricular septum
- Emergency cardiac surgery
- Hemolysis
- Infection, fever, septicemia, abscess, endocarditis
- Injury to mitral valve
- Mechanical failure of delivery system, and/or accessories, including balloon rupture and tip separation
- Silent cerebral ischemia, stroke, transient ischemic attack, cognitive impairment
- Structural valve deterioration (wear, fracture, calcification, stenosis)
- Valve deployment in unintended location
- Valve explants
- Valve migration, malposition or embolization requiring intervention
- Valve regurgitation, paravalvular or transvalvular
- Valve thrombosis

### **9.2.1 Risk Minimization**

Product handling and implant procedure guidance are provided in the IFU and training manual, which will be used for device training to minimize risks associated with device use. All cases will be reviewed and approved prior to the procedure to confirm that the subject is an appropriate candidate for the investigational devices. Edwards representative(s) will be present during all implant procedures to provide device-related guidance.

## 10 STATISTICAL ANALYSIS

### 10.1 Analysis Populations

Enrolled subjects will consist of all subjects who sign and date the ICF.

- The As Treated (AT) population is defined to include all enrolled subjects for whom the valve implant procedure was started.
- The Valve Implant (VI) population is the subset of the AT population consisting of all subjects who receive and retain the study valve upon leaving the procedure room. If it is necessary to implant more than one study valve (valve-in-valve), the subject will still be in the VI population..

### 10.2 Sample Size Considerations

The success criterion for this study is procedural success of at least 90%. The primary statistical analysis for this study is to estimate the procedure success rate. With a sample size of at least 55 subjects, if the observed rate is at least 90%, the lower bound of the observed 95% CI (calculated from binomial distribution) will be at least 80%.

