## PROTOCOL SYNOPSIS

Title	A Prospective, Single-arm, Multicenter Study of the SAPIEN 3 Ultra System in Intermediate Risk Patients with Severe, Calcific, Aortic Stenosis Requiring Aortic Valve Replacement
Objective	To confirm the procedural safety and performance of the SAPIEN 3 Ultra System in subjects with severe, calcific aortic stenosis who are at intermediate operative risk for standard aortic valve replacement (AVR)
Study Device	SAPIEN 3 Ultra Delivery System with the SAPIEN 3 Ultra THV (20, 23 and 26 mm) and SAPIEN 3 THV (29 mm)
Study Design	Prospective, single-arm, multicenter study
Study Population	Subjects with symptomatic, severe, calcific, aortic stenosis requiring AVR who are at intermediate operative risk and have appropriate iliofemoral anatomy for transfemoral access.
Sample Size	Up to 110 subjects who have the procedure started
Study Sites	Up to 8 actively enrolling sites
Assessment Schedule	Screening, procedure, post-procedure, discharge, 30 days, 6 months and annually through 5 years
Primary Endpoint	The primary endpoint is procedural success defined as freedom from all of the following at exit from the procedure room: 

• Mortality

• Conversion to surgery

• Moderate or severe paravalvular regurgitation

Secondary Endpoints	The following secondary endpoints will be evaluated: 

• Major vascular complications through discharge

• Valve migration or embolization through discharge

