**Statistical Methods**

The success criterion for this study is procedural success of at least 90%. The primary statistical analysis for this study is to estimate the procedure success rate. With sample size of at least 55 subjects, if the observed rate is at least 90%, the lower bound of the observed 95% CI (calculated from binomial distribution) will be at least 80%. Descriptive summary statistics will be provided.

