## 3 STUDY DESIGN

This is a prospective, single-arm, multicenter study. Up to 110 subjects will undergo the procedure at up to 8 participating centers. Subject follow-up will occur at 30 days, 6 months and annually through five years.

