## 11 STUDY ADMINISTRATION

### 11.1 General Study Organization

Edwards is the Study Sponsor and has the overall responsibility for the conduct of the study, including assurance that the study meets the regulatory requirements.

Edwards will be responsible for obtaining appropriate approvals prior to study commencement, selecting investigators, ensuring that sites have IRB/EC approval prior to device shipment, and conducting clinical site monitoring to ensure that subjects are being properly consented and the study is being conducted according to the protocol. Edwards will notify investigative sites of enrollment closure.

Edwards will maintain copies of correspondence, data, shipment of devices, adverse device effects and other records related to the clinical study as appropriate.

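### The promise of a 95% lower bound of at least 80% from 55 subjects upward fails at 60 and 61 subjects under the two-sided exact interval; it holds without exception only from 62

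*Combined protocol and SAP*

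**What the plan says.** Section 10.2 sets the criterion, "The success criterion for this study is procedural success of at least 90"%, and describes the primary analysis as estimation of the procedural success rate. It then gives the only sample-size argument in the plan: "With a sample size of at least 55 subjects, if the observed rate is at least 90%, the lower bound of the observed 95% CI", which is "calculated from binomial distribution) will be at least 80"%. The Statistical Methods entry of the synopsis repeats it: "With sample size of at least 55 subjects, if the observed rate is at least 90"%, with the same 80% bound.

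Neither place names the interval or says whether it is one-sided or two-sided.

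The final sample size is not fixed. The synopsis gives "Up to 110 subjects who have the procedure started", and Section 3 gives "Up to 110 subjects will undergo the procedure at up to 8 participating centers". On stopping enrolment, Section 11.1 says only "Edwards will notify investigative sites of enrollment closure".

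**The concern.** The sentence claims something for every sample size from 55 upward, so a single counterexample makes it false. A claim of this kind is easy to get wrong because the number of successes is an integer. The smallest count that reaches 90% does not rise at every step in the sample size, so the exact lower bound at that count does not rise steadily either. A threshold found by checking 55 alone need not hold at larger sizes.

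At stake is the accuracy of the plan's only precision statement. A study closing at 60 with 54 successes would meet its success criterion exactly and still report a lower bound below the one its protocol promised.

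**Working it through.** **Inputs**

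- Sample size n: 55 or more (Section 10.2), up to 110 (synopsis; Section 3).
- Observed rate: at least 90% (Section 10.2), so the smallest qualifying count is x = ceil(0.9n).
- Confidence level: 95%, from the binomial distribution (Section 10.2).
- Assumption: two-sided exact (Clopper-Pearson) interval, 2.5% in each tail.

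**Formula**

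Lower bound L = the 0.025 quantile of Beta(x, n − x + 1). Equivalently, L is below 80% exactly when P(X ≥ x | n, p = 0.80) exceeds 0.025. The table shows both.

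**The plan's own figure**

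At n = 55, 0.9 × 55 = 49.5, so x = 50 and L = 80.05%. One size lower, 49/54 gives 79.70%. The stated 55 therefore reproduces at that size.

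**Larger sizes**

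| n | x | Observed rate | Lower bound | P(X ≥ x) at p = 0.80 | At least 80%? |
|---|---|---|---|---|---|
| 54 | 49 | 90.74% | 79.70% | 0.0282 | no |
| 55 | 50 | 90.91% | 80.05% | 0.0245 | yes |
| 59 | 54 | 91.53% | 81.32% | 0.0140 | yes |
| 60 | 54 | 90.00% | 79.49% | 0.0308 | **no** |
| 61 | 55 | 90.16% | 79.81% | 0.0271 | **no** |
| 62 | 56 | 90.32% | 80.12% | 0.0238 | yes |
| 70 | 63 | 90.00% | 80.48% | 0.0200 | yes |
| 80 | 72 | 90.00% | 81.24% | 0.0131 | yes |
| 110 | 99 | 90.00% | 82.81% | 0.0038 | yes |

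At n = 59 the smallest qualifying count is 54 (5 failures). At n = 60 it is still 54, because 0.9 × 60 = 54 exactly, so 6 failures are now allowed and the bound drops. The same step at n = 70 does no harm because the bound is higher by then. Checking every n from 55 to 1000, only 60 and 61 fall below 80%.

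**Size of the shortfall**

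- n = 60: 80.00 − 79.49 = 0.51 percentage points.
- n = 61: 80.00 − 79.81 = 0.19 percentage points.
- One more success clears 80% comfortably: 55/60 gives 81.61% and 56/61 gives 81.90%.
- Sizes affected: 2 of 110 − 55 + 1 = 56.
- If n were 60, the probability of exactly 54 successes would be 16.9%, 4.9% or 0.7% at true success rates of 90%, 95% or 97%. These rates are assumed; the plan gives none.

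**Other intervals at n of 55 or more**

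| 95% interval | Sizes below 80% |
|---|---|
| Two-sided exact | 60, 61 |
| Agresti-Coull | 60, 61 |
| Wilson | 60 |
| One-sided exact, mid-P, Wald, Jeffreys | none |

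**The case against.** The strongest objection is that the plan does not name its interval, and under some choices the sentence is true. At n = 60 the bound is 81.21% one-sided exact, 82.41% Wald, 80.55% Jeffreys and 80.36% mid-P. The finding is therefore conditional. The plan's own threshold, however, points to the two-sided exact interval. Going up from n = 50, that interval first passes at 55, whereas one-sided exact and Wald already pass at 50, Jeffreys at 52 and mid-P at 53. This is support, not proof: 44/48 (80.02%) and 45/49 (80.40%) also pass under the exact interval, and Agresti-Coull also switches at 55. But Agresti-Coull fails at 60 and 61 as well, so that reading does not rescue the sentence.

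The second objection is materiality, and it stands. No test, performance goal or decision uses the 80% bound, and the reported interval will come from the actual data. Nothing suggests that the sponsor means to close enrolment at 60 or 61; those sizes are permitted, not planned. Reading the sentence as a rounded planning figure helps at 61, where 79.81% rounds to 80%, but not at 60, where 79.49% rounds to 79%.

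**Conclusion.** The statement is wrong as written, and the error is minor. With the two-sided exact interval it fails at n = 60 and n = 61, by at most 0.51 percentage points, and only when the success count is the smallest that reaches 90%. The lowest bound over all sizes from 55 to 110 is 79.49%. The arithmetic is certain; the choice of interval is an inference from the binomial wording and from the switch at 55. The success criterion and the primary estimate are unaffected.

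**What to change.** In the synopsis (Statistical Methods) and in Section 10.2, name the interval as the two-sided 95% exact (Clopper-Pearson) interval. Then make one of two changes:

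- keep the 80% bound and replace 55 by 62, the size from which it holds without exception; or
- keep 55 and state the bound as at least 79%, which covers the true minimum of 79.49%.

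The second leaves the stated minimum size alone and is the less intrusive. If the sponsor used a different interval, it should be named instead and the threshold checked against it at every size from 55 to 110.

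The cost is wording in two sentences, with no effect on patients, design, endpoint or analysis.
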